5.5 Variables

Table 1. Study variables

Category	Variable name	Conceptual definition	Operational definition	Measuring scale
Sociodemographic	ID Number	ID Number	Personal identification number under which you are registered in the country of origin	Nominal
	Age	Duration of an individual's existence measured in units of time.	Number in years	Continual
	Gender	Categorizes the	1. Female	Nominal

Category	Variable name	Conceptual definition	Operational definition	Measuring scale
		individual according to her biological characteristics.	0. Male 2. Undetermined	
	Nationality	Country of birth	Name of country	Nominal
	Department of Residence	A geographic place to which the municipality or city where the person usually resides belongs.	Name of department	Nominal
	Municipality of residence	Geographic place municipality/city where the person usually resides.	Name of municipality/city	Nominal
	Health Service Provider Institution (IPS)	Place where the screening was performed.	1= Fundación cardioinfantil 2= Fundación Santafé 3= Clínica Colombia 4= Hospital Universitario San Ignacio 5= Fundación Valle de Lili 6= Hospital Pablo Tobón Uribe 7= Hospital Universitario Julio Méndez Barreneche E.S.E.	Nominal, polytomous
	Affiliation regime	Category of affiliation to the health system.	0=Not insured 1=Subsidized 2=Contributory 3=Special 4=Exception	Nominal, polytomous
	Entity Benefit plan administrator (EAPB) or Entity obliged to compensate (EOC)	The entity in charge of health care coverage.	Name of entity	Nominal
Risk Factors	Transfusion of blood products	Administration of hemocomponents before 1996.	0. No 1. Yes	Nominal, dichotomous

Category	Variable name	Conceptual definition	Operational definition	Measuring scale
	The year in which you received the transfusion	Date (year) in which you received the transfusion.	The year in which you received the transfusion	Continual
	Major surgery	Surgical procedure performed in the operating room under general or regional sedation that may require post-procedural in-hospital monitoring.	Abdominal laparotomy: 0. no; 1 Yes Gynecologic surgery of any type: 0. No; 1 Yes Orthopedic surgery of any type: 0. No; 1 Yes Any surgery that required in-hospital post-procedure surveillance for more than 24 hours: 0. 0. No; 1 Yes	Nominal, dichotomous
	Intravenous drug use	Having consumed intravenous drugs at any time.	0. No 1. Yes	Nominal, dichotomous

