	Inhaled or intranasal drug use	Having consumed inhaled drugs at any time.	0. No 1. Yes	Nominal, dichotomous
	Men who have sex with men	Man who has had sex with men.	0. No 1. Yes	Nominal, dichotomous
	Known hepatitis B virus infection	Refer to have a diagnosis of hepatitis B virus.	0. No 1. Yes	Nominal, dichotomous
	Known HIV infection	Refer to HIV diagnosis.	0. No 1. Yes	Nominal, dichotomous
	People who have had tattoos, body piercings, scarification, etc.	Presence of tattoos or piercing or scarification.	0. No 1. Yes	Nominal, dichotomous
	Population deprived of liberty or previously incarcerated persons	Being or having been deprived of liberty in a penitentiary center.	0. No 1. Yes	Nominal, dichotomous
	Liver disorders or disease	A person with abnormal liver	0. No 1. Yes	Nominal, dichotomous

Category	Variable name	Conceptual definition	Operational definition	Measuring scale
		tests or liver disease.		
	Occupational exposure	Healthcare workers or members of public safety (e.g., correctional service officers or police) who have been in contact with blood at work through needlestick or sharps injuries.	0. No 1. Yes	Nominal, dichotomous
	Hemodialysis	A person who has undergone hemodialysis.	0. No 1. Yes	Nominal, dichotomous
	Comorbidities potentially associated with HCV infection.	Diabetes, Ischemic heart disease, Cryoglobulinemia, Chronic renal failure, Sjögren's syndrome, Hypothyroidism, Flat lichen, Rheumatoid arthritis, Non-Hodgkin's lymphoma, Acute lymphoblastic leukemia, Waldenstrom's macroglobulinemia, Chronic renal insufficiency, Sjögren's syndrome	0. No 1. Yes	Nominal, dichotomous
Missed opportunity	Doctor visits	Doctor visits in the last month	How many?	Continued
Sample results	HCV antibody screening test	Report of HCV antibody test result.	0. Non-reactive 1. Reactive	Nominal, dichotomous
	Viral load test	Report the viral load result of those patients who presented reactive HCV antibodies.	0. Non-reactive 1. Reactive	Nominal, dichotomous

Category	Variable name	Conceptual definition	Operational definition	Measuring scale
Follow-up	SIVIGILA Report	The confirmed cases of HCV as a public health event are reported to the surveillance system utilizing form 340.	0: Not reported 1: If reported	Nominal, dichotomous
	Follow-up of confirmed case	Follow-up that each case confirmed in the study has access to consultation by a clinical specialist.	0. No Why? 1. Yes	Nominal, dichotomous

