5.10 Data Analysis Plan

Descriptive analysis will be performed for all variables of interest proposed in this study. Descriptive statistics (frequencies and percentages) will be estimated. For continuous quantitative variables, measures of central tendency (mean and median) and measures of dispersion (variance, standard deviation) will be estimated. Possible relationships between sociodemographic variables, risk factors, and documentation of positive HCV antibodies will be explored, for which a bivariate analysis will be performed using X² (chi-square) tests to explore the proposed associations. All analyses will be performed with Stata version 18.

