12.1 Annex 1. Data collection instrument

Adult screening for hepatitis C and linkage to treatment in Colombian hospitals	
Patient's name:	Identification number:
Age (in years):	Sex: Male: ___ Female: ___
Contact phone number:	Residence address: Department of Residence: Municipality of residence:
Affiliation scheme: 0. Uninsured: _____ 1. Subsidized: _____ 2. Contributory: _____ 3. Special: _____ 4. Exception: _____	Institución prestadora de servicio de salud (IPS): Fundación cardiointantil _____ Fundación Santafé _____ Clínica Colombia _____ Hospital Universitario San Ignacio _____ Fundación Valle de Lili _____ Hospital Pablo Tobón Uribe _____ Hospital Universitario Julio Méndez Barreneche E.S.E. _____
E-mail: _____ Nationality: _____	
Received blood transfusion before 1996: YES ___ NO ___	Year of transfusion:
Name of EAPB or Entity obliged to compensate:	Major Surgery: Yes ___ No ___ Type of surgery: Abdominal laparotomy: Yes ___ No ___ Gynecologic surgery of any type: Yes ___ No ___ Orthopedic surgery of any type: Yes ___ No ___ Any surgery that has required post-procedure in-hospital surveillance: Yes ___ No ___
Tattoos: Yes ___ No ___	Intravenous drug user: Yes ___ No ___ Nasal drug user: Yes ___ No ___
Man who has sex with men: Yes ___ No ___	Known hepatitis B virus infection: Yes ___ No ___
Known HIV infection: Yes ___ No ___	Have you ever had tattoos or body piercings? Yes ___ No ___
Abnormal liver tests or with liver disease:	Healthcare workers or members of public

Yes__ No__	safety (e.g., correctional service officers or police) who have come into contact with blood at work through needle sticks or sharps injuries: Yes__ No__
A person who has undergone hemodialysis: YES__ NO__	Diagnosis of diabetes: YES__ NO__
Diagnosis of Cryoglobulinemia: YES__ NO__	Diagnosis of coronary artery disease: YES__ NO__
Diagnosis of renal failure: YES__ NO__	
Population deprived of liberty or previously incarcerated persons: YES __NO__	
HCV antibody detection test: Non-reactive: _____ Reactive: _____	
Viral load test: Positive: _____ Negative: _____ Not applicable: _____(in all cases where HCV antibody screening test is non-reactive).	
Case reported to Sivigila YES__ NO__	
The positive case has been followed up YES __NO__	
The patient has had access to a specialized consultation YES __NO__ Why?	
The patient was able to access treatment YES __NO__ Why?	
Date of completion:	
Name of the person doing the diligence:	

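### Sex between men and gynecologic surgery have only No/Yes codes and 5.10 sets no restriction by sex, so their tests against antibody status may partly measure a sex difference in HCV

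*Combined protocol and SAP*

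**What the plan says.** The study population in section 5.2 is adults of both sexes. One specific objective in 4.2 is an exploratory look at the association between positive cases and the risk factors. Section 5.10 sets the scope of that look: "Possible relationships between sociodemographic variables, risk factors, and documentation of positive HCV antibodies will be explored". The same section names a single method for the task, namely that "a bivariate analysis will be performed using X² (chi-square) tests to explore the proposed associations". It restricts no exposure to one sex, and it mentions neither stratification nor adjustment.

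Table 1 in section 5.5 defines one risk factor as "Man who has had sex with men", with codes 0 and 1 only, and classes it as dichotomous. Under major surgery, one of four items is "Gynecologic surgery of any type: 0. No; 1 Yes". The form in Annex 1 repeats both as two-way fields: "Man who has sex with men: Yes ___ No" and "Gynecologic surgery of any type: Yes ___ No".

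Annex 1 does have a third option for the viral load result: "Not applicable: _____(in all cases where HCV antibody screening test is non-reactive". No such option is given for the two sex-specific items, and no instruction says how a woman's or a man's form is to be completed there. Sex is recorded on the same form.

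**The concern.** A comparison group should consist of people who could have had the exposure. If a woman's form reads No for sex between men, she joins the unexposed group although she could never have been exposed. The same holds for a man and gynecologic surgery. The exposed group is then all of one sex and the unexposed group is mixed, so any sex difference in antibody prevalence enters the association.

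An exposure with no effect could then look like a risk factor or look protective, and a real effect could be inflated or hidden. The result on sex between men is likely to be read closely: the background reports 72.1% of Colombian cases as probably sexually transmitted, cites testing recommendations specific to this group, and names stigma as a barrier to diagnosis.

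**Working it through.** **The plan's own figure.** The documents give no number for the association analyses. The only related figure is the sample size in 5.8, which reproduces: n = 3 × 280,186 × 0.25 / [(0.05² / 1.96²) × 280,185 + 0.25] = 1,150.9, rounded up to 1,151 per institution. It is used here only to judge counts. Seven institutions are listed, and 7 × 1,151 = 8,057 is an assumed total.

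**Assumed inputs; none is in the documents.** 55% women and 45% men; 4% of men report sex with men; 35% of women have had gynecologic surgery; neither exposure has any effect within its own sex; the other sex is coded No. Antibody prevalence is pM in men and pW in women.

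**Formulas for the crude prevalence ratio, exposed over unexposed.**
- Sex between men: pM ÷ [(0.55 pW + 0.45 × 0.96 pM) / (0.55 + 0.45 × 0.96)]
- Gynecologic surgery: pW ÷ [(0.55 × 0.65 pW + 0.45 pM) / (0.55 × 0.65 + 0.45)]

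**With pM = 1.25% and pW = 0.75%.**
- Sex between men: unexposed prevalence = (0.4125 + 0.5400) / 0.982 = 0.970%; ratio = 1.25 / 0.970 = 1.29.
- Gynecologic surgery: unexposed prevalence = (0.2681 + 0.5625) / 0.8075 = 1.029%; ratio = 0.75 / 1.029 = 0.73.

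**Other prevalences, same formulas.**

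| Prevalence, men / women | Sex between men | Gynecologic surgery |
|---|---|---|
| 1.25% / 0.75% | 1.29 | 0.73 |
| 0.75% / 1.25% | 0.73 | 1.29 |
| 2 : 1 | 1.39 | 0.64 |
| 1 : 2 | 0.64 | 1.39 |
| equal | 1.00 | 1.00 |

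Restricted to the sex that can be exposed, every entry is 1.00.

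**What this does to the test.** With 8,057 participants and 1.25% / 0.75%, 8,057 × 0.45 × 0.04 = 145 men are exposed. They yield 145 × 1.25% = 1.8 positives. Overall prevalence is 0.45 × 1.25% + 0.55 × 0.75% = 0.975%, so independence predicts 145 × 0.975% = 1.4. The excess is 0.4 of a case. Simulating the uncorrected chi-square at the nominal 5% level gives false-positive rates of about 9% for sex between men and 15% for gynecologic surgery tested alone. With the prevalences reversed the rates are about 2% and 18%. Restricted to the sex at risk they are about 4 to 5% for both exposures.

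**Pre-1996 transfusion, for comparison.** Assume 8% exposed among those born before 1996, prevalence 1% in them and 0.2 to 0.5% in those born later, and no effect. The same reasoning gives 1.09 to 1.34 if 15 to 30% of the sample were born in 1996 or later, and 1.03 to 1.09 if 5 to 10% were. A ratio of 1.00 after restriction by birth year requires flat prevalence by age among those born earlier, which cannot be assumed.

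**The case against.** The strongest reply is that the key step is inferred. No sentence says the other sex is coded No, and none says the tests use the whole sample. A blank treated as missing would remove the problem. This stands as a limit: a reader might infer that the protocol orders women to be counted as unexposed, and it does not. But a dichotomous 0/1 variable with no missing-data rule, put into an unrestricted test, leads there if followed literally.

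Second, gynecologic surgery is one of four items under a single variable. If only composite major surgery is tested, the ratios above do not apply and the distortion is diluted. That also stands, although the composite still contains an item that only women can have.

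Third, the sizes rest on assumptions, 5.10 names a test rather than a ratio, and the bias is zero if the sexes have equal prevalence. All true. At one institution's 1,151 participants, about 21 men would be exposed (1,151 × 0.45 × 0.04), with fewer than one expected positive, so sparse cells would matter more there than this bias.

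Fourth, a reader might treat transfusion, defined as "Administration of hemocomponents before 1996", as the same fault by birth year. Only part of it is: people born in 1996 or later cannot be exposed, but the rest is ordinary confounding by age, which restriction by birth year leaves in place.

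**Conclusion.** The point holds as an unspecified denominator that, under the most literal reading of the plan, lets a sex difference in prevalence enter two risk-factor associations. It depends on the other sex being entered as No and on prevalence differing by sex. Under the assumptions shown, a null exposure would give ratios from about 0.73 to 1.29, or from 0.64 to 1.39 with a two-fold sex difference. The direction cannot be predicted from the documents. For gynecologic surgery the figures apply only if that item is tested separately.

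A reader might go further and conclude that the study's prevalence result is biased, or that a false finding on sex between men is likely. The documents support neither. The prevalence objective, the sample size and the access-to-care objective do not use these comparisons, and the expected excess among exposed men is a fraction of one case. The point deserves correction because it bears on a stated objective and the remedy needs no new data.

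**What to change.** Add to 5.10 that sex between men is analysed among men only and that gynecologic surgery, if tested separately, is analysed among women only. If composite major surgery is tested, stratify it by sex. Say in the same place how a blank in either field is handled.

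Treat pre-1996 transfusion separately: restrict it to people born before 1996, using recorded age and the form's completion date, and stratify by age as well.

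The cost is a few sentences. Sex and age are already collected, so all of this can be done at analysis even if forms are in use, and no participant who could have been exposed is lost. A not-applicable code for the two fields in Table 1 of section 5.5 and in Annex 1 would make the intent clear but is optional.

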According to information from the High-Cost Account (CAC for its acronym in Spanish), between January 1st and December 31st, 2021, 962 persons with the infection were identified in Colombia (13). According to the probable mechanism of transmission, the highest proportions are sexual transmission (72.1%) and parenteral/percutaneous (11.8% of cases) (14). According to information published by the Polaris Observatory up to 2021, there is a prevalence of 0.67% (320,000 cases), 10% of cases have been diagnosed, and of these <1% have been treated and 2639 deaths have been registered annually. According to their predictions with the current behavior, it is estimated that by the year 2051 Colombia will achieve the goals established by the WHO (15).

Three-quarters of HCV-infected people live in low- to middle-income countries, some of

which lack budgets for screening, diagnosis, and treatment campaigns. In 2018, Polaris Observatory reported that only 12 countries were on schedule to meet HCV elimination targets by 2030, these countries were Australia, Egypt, France, Georgia, Iceland, Italy, Japan, Mongolia, the Netherlands, Spain, Switzerland, and the United States (6).

Prevalence studies for HCV have been conducted in less than half of the countries in Latin America, and most of them are of poor-quality design. Extrapolating data from countries with registries, the estimated HCV prevalence rate in Latin America is less than 1%. Estimates made by the Polaris Observatory, according to epidemiological data from the online database in 2019, several countries were able to diagnose a significant percentage of the population with HCV infection; however, only Brazil was able to treat the required number of patients to achieve an annual net cure of more than 1% of those infected (16).

A study modeling the impact of DAA treatment on the course of HCV infection showed that achieving the WHO 2030 targets would require a net cure of 7% per year from 2016. "Net cure" was defined as the number of persons with sustained virologic response, minus new HCV infections, plus HCV-related deaths (17).

The American Association for the Study of Liver Diseases (AASLD), the Infectious Diseases Society of America (IDSA), and the Center for Disease Control (CDC) recommend one-time, routine, opt-out HCV screening for all persons aged 18 years and older. Additionally, (18):

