4.2 Specific objectives

- Characterize the study population socio-demographically.
- Describe the epidemiological characteristics of HCV antibody-positive patients.

- Determine the proportion of patients with positive HCV antibodies and positive viral load (quantitative) for HCV.
- Perform an exploratory analysis of the association of positive cases and the different risk factors for HCV infection.
- Quantify how many HCV-positive individuals were able to access the management pathway and treatment.

5 Methodology

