5.8 Sample size

Considering that the prevalence of HCV in the hospital population with risk factors is unknown, 50% will be considered, with a confidence level of 95%, an error of 5%, a design effect of 3, and a population served on average for the institutions included of 280,186 during 2021, the minimum sample size required per institution is 1,151 and the maximum with a confidence level of 99.99% is 4,519 (Table 1).

Table 1. Sample size for frequency in a population

Population size (for finite population correction factor or fcp)(N):	280.186
Hypothetical % frequency of the outcome factor in the population (p):	50%+/-5
Confidence limits as % of 100(absolute +/-%)(d):	5%
Design effect (for group surveys-EDFF):	3

Sample Size (n) for Various Confidence Levels	
Confidence Interval (%)	Sample size
95%	1151
80%	493
90%	811
97%	1411
99%	1986
99.90%	3236
99.99%	4519

Sample size $n = [EDFF * Np(1-p)] / [(d^2 / Z^2(1-\alpha/2)^2 * (N-1) + p*(1-p)]$.

Source: Results from OpenEpi, version 3, the SSPropor open-source calculator.

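### Section 5.10 relies on chi-square alone, with no rule for sparse tables, so some exploratory risk-factor p-values could be unreliable (minor, cheap to fix)

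*Combined protocol and SAP*

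**What the plan says.** Section 4.2 lists this aim among the specific objectives: "Perform an exploratory analysis of the association of positive cases and the different risk factors for HCV infection". Section 5.10 takes it up: "Possible relationships between sociodemographic variables, risk factors, and documentation of positive HCV antibodies will be explored, for which a bivariate analysis will be performed". It names one method: "bivariate analysis will be performed using X² (chi-square) tests to explore the proposed associations". The outcome there is antibody positivity, and the explanatory variables are the sociodemographic items and the risk factors. Section 5.10 also promises frequencies and percentages for all variables and names the software ("All analyses will be performed with Stata version 18").

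It does not mention an exact test, a continuity correction, a minimum expected count, a rule for merging categories, an effect estimate with an interval, or a significance level.

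Three other places determine how sparse the tables may be:
- Section 5.8: "the minimum sample size required per institution is 1,151". Table 1 in section 5.5 lists seven institutions.
- The introduction, for Colombia: "there is a prevalence of 0.67% (320,000 cases". It also puts Latin America below 1%.
- Table 1 in section 5.5 records department, municipality, nationality and insurer as names, for example "Name of municipality/city". Each can take many values.

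**The concern.** The chi-square p-value is a large-sample approximation. It can fail when very few positives are expected in a cell. A rare outcome crossed with a very rare exposure, or with a variable that has dozens of small levels, produces such cells. If 5.10 is followed literally, one chance positive in a very small group can be reported as an association, and a municipality or insurer table can appear significant with nothing behind it. Section 7 plans to present the results to clinicians, insurers and decision makers. A p-value without an effect size and interval would not show those readers how little data lay behind it.

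**Working it through.** **Inputs.** From the documents: 1,151 per institution and N = 280,186 (section 5.8); seven institutions (section 5.5); 0.67% and under 1% (introduction). Assumed, because the documents do not give them: positivity of 0.67-1% in the study sample, a two-sided 0.05 level, the uncorrected Pearson form of chi-square, and the exposure group sizes.

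**1. The plan's own sample size reproduces.** n = DEFF·N·p(1-p) / [(d²/z²)(N-1) + p(1-p)] = 3 × 280,186 × 0.25 / [(0.0025/3.8415) × 280,185 + 0.25] = 210,139.5 / 182.59 = 1,150.9, stated as 1,151.

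**2. Expected positives.** The pooled minimum is 7 × 1,151 = 8,057. 8,057 × 0.0067 = 54 and 8,057 × 0.01 = 81.

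**3. Where the expected exposed-positive count falls below 5.** With m positives, it reaches 5 when the exposed share is 5/m: 5/54 = 9.3% and 5/81 = 6.2%.

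**4. One positive among k exposed.** X² = n(ad - bc)² / [k(n-k)m(n-m)], with n = 8,057 and m = 81.
- k = 17: a=1, b=16, c=80, d=7,960, so ad - bc = 6,680 and X² = 8,057 × 6,680² / (17 × 8,040 × 81 × 7,976) = 4.07, p = 0.044. Fisher's exact p = 0.158.
- k = 18: ad - bc = 7,959 - 1,360 = 6,599 and X² = 3.75, p = 0.053.
- k = 10: Pearson p = 0.004, Fisher p = 0.096.

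One positive therefore gives Pearson p<0.05 in every group of up to 17 people; Fisher's test does so only up to 5. With 54 positives the limits are 26 and 7.

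**5. Exact size of the nominal 5% Pearson test.** This is the hypergeometric probability that X² exceeds 3.841 when there is no association. At k = 17 a single exposed positive is enough, so the size is P(X ≥ 1) = 15.8%. At k = 18 two are needed, and the size drops to 1.4%.

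| Positives | Exposed (k) | Expected count, k × m/n | Exact size |
|---|---|---|---|
| 81 | 8 | 0.08 | 7.8% |
| 81 | 17 | 0.17 | 15.8% |
| 81 | 18 | 0.18 | 1.4% |
| 81 | 40 | 0.40 | 6.1% |
| 81 | 81 | 0.81 | 4.8% |
| 81 | 121 | 1.22 | 3.3% |
| 81 | 403 | 4.05 | 6.4% |
| 54 | 26 | 0.17 | 16.1% |
| 54 | 27 | 0.18 | 1.4% |
| 54 | 81 | 0.54 | 10.2% |

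The pattern is a sawtooth. Size exceeds 7.5% only at k = 8-17, 46-55 and 98-102 with 81 positives, or k = 12-26, 68-82 and 147-154 with 54.

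**6. Sensitivity to positivity and sample size.** At 2% positivity (161 positives) the largest group in which one positive gives p<0.05 is 8 people, with size 14.9%. At 5% (403 positives) it is 3 people, with size 14.3%. At the maximum sample of 7 × 4,519 = 31,633 and 1% positivity it is again 17 people, with size 15.7%.

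**7. Many-level variables.** The documents give no level frequencies, so these had to be assumed. With 81 positives and 60-350 levels, simulated rejection under no association was about 13-31% at nominal 5%. Another set of assumed distributions (a few large categories and many small ones, 53-363 levels) gave 20-35%. The direction is stable; the exact figure depends on the assumed shape.

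**The case against.** The strongest reply is that the problem is narrow and rests on assumptions. Much of that stands.

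- **Positivity may be higher.** The cited percentages describe general populations, section 5.8 calls the target prevalence unknown, and section 2 expects more infection among people with risk factors. The outcome in 5.10 is antibody positivity, which also counts people without current viremia. Higher positivity shrinks the affected groups (step 6) but does not remove them.
- **The 10-16% figures are peaks.** One more exposed person takes 15.8% to 1.4%. They should be read as the upper end of a swing, not as a typical error rate.
- **The text says chi-square, not Pearson.** With Yates' correction, p at 17 exposed would be 0.42, and size stayed at or below about 5% in the cases checked. The plan does not specify the correction.
- **The analysis is exploratory and the design descriptive.** That lowers the severity. It does not make the unsuitable test the right one to write down.

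A reader might also infer more than the documents support:
- *That most exposed-positive cells are too sparse.* No exposure frequencies are given. Common items such as surgery, tattoos or the combined comorbidity variable may pass comfortably in pooled data.
- *That an expected count below 5 means inflated error.* It does not: 403 exposed gives an expected count of 4.05 and a size of 6.4%, and 121 exposed gives 3.3%.
- *That single-hospital tables are worse still.* They would be, but 5.10 plans no hospital-level association tests. Section 5.9 promises only reports to each institution.
- *That adjusted or penalised regression is needed.* The stated objective is exploratory and bivariate, so adjustment is a preference rather than a correction.

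**Conclusion.** The point holds as a minor one. Section 5.10 commits every association to chi-square with no fallback, and foreseeable tables are too sparse for the uncorrected version, chiefly those for very rare exposures and for many-level sociodemographic variables. For a binary factor the true error rate of a nominal 5% test lies anywhere from about 1% to 16%, depending on the exact group size. For many-level variables it is roughly 13-31% under assumed distributions. These sizes rest on 0.67-1% positivity, the pooled minimum of 8,057, a 0.05 level and the uncorrected test, none of which the plan fixes for this analysis except the minimum sample. Interpretation of the exploratory risk-factor objective is affected. The main prevalence estimate is not.

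**What to change.** Add to section 5.10:
1. Use Fisher's exact test, or a mid-p version, whenever any expected count is below 5. This threshold is a convenient trigger, not a claim that chi-square always fails below it.
2. Merge municipality, department, nationality and insurer into a few groups named in advance, or describe them without testing.
3. Report cell counts and unadjusted odds ratios with exact 95% confidence intervals beside each p-value.

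The cost is a few sentences, with no new data and no design change. The downside is that Fisher's test is conservative in sparse tables: its true size is about 1% at 17 exposed with 81 positives, so weak associations will be harder to detect. Mid-p is less conservative.
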